8.5.6 Pregnancy Reporting

Any pregnancy of a subject or a subject's partner that is reported while participating in the study will be monitored for the full term and or followed until the outcome of the pregnancy is known. Pregnancy-associated SAEs will be processed and submitted as necessary, as per the suspected unexpected serious adverse reactions (SUSAR) reporting process described in the following section.

8.5.7 Communication Plan

Ultragenyx or its designee will submit SUSAR reports to appropriate regulatory authorities and investigators as per local laws and regulations. Fatal and life-threatening SUSARs will be submitted no later than 7 calendar days of first knowledge of the event and follow-up information will be submitted within an additional eight (8) days. All other SUSARs will be submitted within 15 calendar days of first knowledge of the event.

Principal Investigators are required to report any urgent safety matters to Ultragenyx or its designee within 24 hours. Ultragenyx or its designee will inform the regulatory authorities and investigators of any events (e.g., change to the safety profile of KRN23, major safety findings) that may occur during the clinical trial that do not fall within the definition of a SUSAR but may affect the safety of subjects participating in the clinical trials, as required in accordance with applicable laws and regulations. The reporting period for urgent safety issues is the period from signing the informed consent through 12 weeks following the last dose of study drug.

The investigator is responsible for notifying the IRBs of SAEs and any urgent safety matters, in accordance with IRB requirements and local laws and regulations. A copy of this notification must be provided to Ultragenyx or its designee.

Non-SUSARs will be maintained in the Ultragenyx safety database and provided in annual and/or periodic reports as per local laws and regulations. Ultragenyx or its designee will prepare and submit annual safety reports and/or other aggregate periodic summary reports to regulatory authorities, as required

8.6 Financing and Insurance

Financing and insurance for this clinical trial will be addressed in clinical trial agreements with the study site.

8.7 Publication Policy

Any publication or presentation by the investigator and/or the Institution based on data or results resulting from the Ultragenyx study shall only be done in strict accordance with the

Protocol Number: UX023-CL203
Amendment 2
29 September 2017

Publication section in the Clinical Trial Agreement executed between Ultragenyx and the Institution and/or the investigator.

## STATISTICAL ANALYSIS PLAN AMENDMENT

### SUMMARY OF CHANGES

#### UX023-CL203 Amendment 1

27 April 2016

---

The UX023-CL203 statistical analysis plan (dated 15 January 2016) has been amended. Important changes in Amendment 1 are summarized below:

1. **Interim Analysis Timing:** Section 3.6 has been updated to reflect the timing of the interim analysis to support regulatory submission.
2. **Events to Monitor:** Section 8.6.1 has been updated so that the events to monitor categories are consistent with the product identified or potential risks.
3. **Analysis of Vital Signs:** Section 8.6.6 has been updated to reflect the standard descriptive analysis for vital signs.
4. **Analysis of ECG:** Section 8.7.2 has been updated to remove the normality or abnormality analysis of the ECG tracing because the overall interpretation of ECG is not collected for the study.
5. **6-Minute Walk Test:** Section 8.8.2.3 has been updated to remove the graph display of 6-minute walk test data because there is only one post-baseline time point (Week 24).

## ABBREVIATIONS

1,25[OH] 2 D	1,25-dihydroxyvitamin D
3MSCT	3-Minute Stair Climb Test
6MWT	6-Minute Walk Test
AE	Adverse event
ALP	Alkaline phosphatase
BALP	Bone-specific alkaline phosphatase
BMI	Body mass index
BPI	Brief Pain Inventory
CFB	Change from Baseline
CTX	Carboxy terminal cross-linked telopeptide of type I collagen
FGFR1	Fibroblast growth factor receptor 1
FGF23	Fibroblast growth factor 23
GEE	Generalized Estimating Equations
GFR	Glomerular filtration rate
HAHA	Anti-KRN23 antibody
HQRL	Health-related quality of life
iPTH	Intact parathyroid hormone
ISR	Injection site reactions
LVH	Left ventricular hypertrophy
mAb	Monoclonal antibody
MedDRA	Medical Dictionary for Regulatory Activities
P1NP	Procollagen type 1 N-terminal propeptide
PD	Pharmacodynamic
PHEX	Phosphate-regulating gene with Homologies to Endopeptidases on the X-chromosome
PRO	Subject-reported outcome
QOL	Quality of life
QTc	Corrected QT interval
SAE	Serious adverse event
SC	Subcutaneous
SF-36	36-item Short Form Health Survey
SMQ	Standardised MedDRA Query
TEAE	Treatment-emergent adverse event
TmP/GFR	Ratio of renal tubular maximum phosphate reabsorption rate to glomerular filtration rate
TRP	Tubular resorption of phosphate
TUG	Timed up and go
WHO	World Health Organization
WOMAC	Western Ontario and McMaster Universities Osteoarthritis Index
XLH	X-Linked Hypophosphatemia

## 1 INTRODUCTION

The purpose of this statistical analysis plan is to provide details of the statistical analyses that have been outlined within the original UX023-CL203 Protocol dated 05 September 2014. The data collected in this study will evaluate the safety and pharmacodynamics of KRN23 in adult subjects with X-Linked Hypophosphatemia.

## 2 STUDY OBJECTIVES

### 2.1 Primary Safety and Pharmacodynamics

The primary objectives of this study are to:

- Assess the long-term safety of KRN23 SC administration in adult subjects with XLH
- Assess the proportion of subjects achieving serum phosphorus levels in the normal range (2.5-4.5 mg/dL) with long-term administration of KRN23
- Assess long-term PD of KRN23 as measured by changes in the following:
  - Serum and urinary phosphorus
  - TmP/GFR and TRP
  - Serum 1,25(OH)2D
  - Serum FGF23
  - Bone biomarkers: serum ALP, bone-specific ALP (BALP), carboxy terminal cross-linked telopeptide of type I collagen (CTX), and procollagen type 1 N-terminal propeptide (P1NP)
- Assess long-term immunogenicity of KRN23 as measured by presence of anti-KRN23 antibody (HaHa)

### 2.2 Efficacy

The efficacy objectives of this study are to:

- Evaluate changes in underlying skeletal disease by standard radiographs of the legs, feet, and lateral spine as well as any location(s) where the subject is currently experiencing tenderness or pain that may reflect underlying pathology, or where the subject has a history of recent (< 3 months) fracture
- Evaluate changes in subject-reported outcomes (PROs) and physical function outcomes including:
  - Subject-reported pain – Brief Pain Inventory (BPI)
  - Disability – Western Ontario and McMaster Universities Osteoarthritis Index (WOMAC)
  - Quality of life (QOL) scores – 36-item Short Form Health Survey (SF-36)
  - Walking ability – 6-Minute Walk Test (6MWT)
  - Balance and agility – Timed Up and Go (TUG) Test

Due to the inability to standardize the number of stairs used for testing at all study sites, the 3MSCT was not collected in this study and is excluded from the final and interim analyses.

### 3 STUDY DESIGN

#### 3.1 Overall Study Design and Plan

This study is a Phase 2b, open-label, long-term extension study of the completed studies KRN23-INT-001 and KRN23-INT-002 in adult subjects with XLH. The study population will consist of approximately 25 eligible subjects who participated in Kyowa Hakko Kirin Pharma, Incorporated's study KRN23-INT-001 or study KRN23-INT-002 (received at least 2 doses of KRN23). Subjects who were discontinued from KRN23-INT-001 or KRN23-INT-002 due to a TEAE classified as possibly or probably related to treatment may be eligible for participation in this study based on the clinical judgment of the investigator with agreement from the sponsor. The study will be conducted over 72 weeks to assess the long-term safety, immunogenicity, PD, and clinical efficacy of KRN23.

The starting dose of KRN23 at Baseline (Week 0) in this study will be individual for each subject, i.e., the same as a subject's last dose in studies KRN23-INT-001 or KRN23-INT-002 (0.30, 0.60, or 1.0 mg/kg). Dosing will occur at the clinic and the volume will be based on the weight obtained on Day 0.

Up to Week 12, individual subjects who have not reached serum phosphorus levels above the lower limit of normal (LLN; 2.5 mg/dL) at the end of the dose interval may have their doses titrated every 4 weeks to a maximum dose of 1.0 mg/kg based on fasting trough serum phosphorus levels. Doses may be titrated downward if at any point the serum phosphorus level increases above the upper limit of normal (ULN; 4.5 mg/dL). KRN23 injections will be repeated every 4 weeks for the duration of the study (from Week 0 through Week 68), and weight will be reassessed periodically for dose volume adjustments as needed.

A complete schedule of events is included in [Appendix 6](#).

#### 3.2 Study Duration

The planned duration of treatment in this study will be 72 weeks.

#### 3.3 Randomization and Blinding Method of Assigning Subjects to Treatment Groups

All subjects received KRN23 on an open-label basis. Randomization and blinding are not applicable in this study.

#### 3.4 Stratification Factors

Not applicable.

### **3.5 Determination of Sample Size**

The rationale for the sample size for this open-label extension study is based on practical considerations to obtain the needed information to meet study objectives. The sample size of this study is based on the number of subjects who have satisfactorily completed studies KRN23-INT-001 and/or KRN23-INT-002, along with the other eligibility criteria, and have agreed to participate in this long-term extension study. Approximately 25 subjects may be enrolled in this study. Subjects who were enrolled in the KRN23-INT-002 bone sub-study and who received KRN23 are also eligible. Since this is an exploratory study, no formal statistical power and sample size estimation methods were used to determine the sample size; therefore, the current study design is not powered to assess a pre-defined statistical difference in any endpoint.

### **3.6 Week 24 Analysis**

Week 24 analysis will be conducted after all subjects have completed the Week 24 visits or discontinued the study. The purpose of this analysis is to potentially provide supporting data to any regulatory filings of UX023 in XLH.

Additional interim analyses may be conducted if deemed necessary.

### **3.7 Data Monitoring Committee**

Based on the open-label study design, safety will be monitored by Ultragenyx. An independent data monitoring committee will not be used.

## 4 STUDY CLINICAL OUTCOMES AND COVARIATES

### 4.1 Safety Endpoints

Safety assessments will be summarized at Baseline and at each observed time that they are collected. In addition to the incidence and frequency of AEs, the following endpoints will be examined as CFB:

- Number of clinically significant changes in vital signs, laboratory tests, physical examinations, ECHO and ECG, and renal ultrasounds
- Number of subjects who develop anti-KRN23 antibodies

### 4.2 Pharmacodynamics Endpoints

The primary pharmacodynamics endpoints are:

- Number and percentage of subjects who have serum phosphorus levels which, at any time after dosing are in the normal range ( $\geq 2.5$  and  $\leq 4.5$ ) or outside the normal range
- Change from baseline in serum biochemistry parameters associated with XLH, as measured by serum phosphorus, iPTH, FGF23 (total and free), and  $1,25(\text{OH})_2\text{D}$
- Change from baseline in urinalysis parameters associated with XLH, as measured by 2-hour urine TmP/GFR and TRP, i.e., calcium, creatinine, and phosphorus
- Change from baseline in urine parameters associated with XLH, as measured by 24-hour urine, i.e., urinary phosphate, calcium, creatinine, and urine calcium/creatinine ratio
- Change from baseline in bone biomarkers associated with XLH, as measured by total ALP and BALP, CTx, and P1NP
- Change from baseline in fractional excretion of phosphorus (FEP), defined as  $100\% * (2\text{-hour urine phosphorus} * \text{serum creatinine}) / (2\text{-hour urine creatinine} * \text{serum phosphorus})$

### 4.3 Efficacy Endpoints

The exploratory efficacy endpoints are:

- Change from baseline in pain and health-related QoL as measured by changes in the WOMAC, BPI, and SF-36 scores
- Healing of prior or existing fractures or other disease-related skeletal abnormalities as viewed on standard radiographs
- Change from baseline in walking ability as measured by change in the distance walked on the 6MWT in meters and percent predicted normal values
- Change from baseline in transitions during ambulatory activity that incorporates strength, agility, and dynamic balance as measured by the time required to complete the TUG test.

## 5 DEFINITIONS AND DERIVED EFFICACY VARIABLES

### 5.1 Baseline

Baseline is defined as the last non-missing measurement taken prior to the first dose of study drug administration in CL203 study.

Note that all subjects enrolled in this study received at least 2 doses of KRN23 in Kyowa Hakko Kirin Pharma, Incorporated's study KRN23-INT-001 or study KRN23-INT-002; however, since a minimum of 21 months separated the last dose in KRN23-US-001/002 studies and the first dose in this study, values measured in KRN23-INT-001 or KRN-INT-002 studies will not serve as baseline values for this study.

### 5.2 First KRN23 Dose Date

First KRN23 dose date refers to the first dose of KRN23 given in UX023-CL203 study. First dose date will not take into account KRN23 doses given in studies KRN23-US-02, KRN23-INT-001 or KRN23-INT-002.

### 5.3 BPI

The BPI will be completed by subjects to assess pain severity and the impact of pain on daily functioning.

The BPI endpoints to be analyzed are as follows:

- Worst pain, defined as the answer to question 3 (pain at its worst in the last 24 hours)
- Pain severity, defined as the average of questions 3 through 6
- Pain interference, defined as the average of questions 9A through 9G regarding “pain interfered” in the last 24 hours.

[Appendix 2](#) includes the complete text of the BPI. Of note, subjects enrolled in this study were not asked questions 7 and 8, therefore the answers to these questions are not used for analysis in this study.

### 5.4 WOMAC

The WOMAC will be completed by subjects to assess pain, stiffness, and physical function. The WOMAC consists of 24 items divided into 3 subscales:

- Pain (5 items): during walking, using stairs, in bed, sitting or lying, and standing
- Stiffness (2 items): after first waking and later in the day
- Physical Function (17 items): stair use, rising from sitting, standing, bending, walking, getting in / out of a car, shopping, putting on / taking off socks, rising from bed, lying in

bed, getting in / out of bath, sitting, getting on / off toilet, heavy household duties, light household duties.

The 24-question self-reported WOMAC evaluates the condition of the knee, hip, and other joints in osteoarthritis, measuring three dimensions: Pain, Stiffness, and Physical Functioning (Table 1) over the previous 48 hours.

**Table 1: WOMAC Scales, Number of Questions in Each Scale, and Scores from a General Population**

Scale Name	Number of WOMAC questions combined into scale score	Normative values from general population 	
		Mean*	Standard Deviation*
Pain	5	14.1	19.7
Stiffness	2	20.1	23.6
Physical Functioning	17	15.4	20.2

\* The published values are on a 0-10 scale and were converted here to a 0-100 scale by multiplying by 10.

All questions are measured on a 5-point Likert scale: none (0), mild (1), moderate (2), severe (3), and extreme (4). Scoring is a simple sum, so Pain scores could range from 0 to 20, Stiffness from 0 to 8, and Physical Functioning from 0 to 68, with higher numbers indicating worse condition. Scores are then normalized to a 0-100 metric representing the percent of the maximum score, where 0 was the best health state and 100 the worst.

WOMAC scores are not norm-based, so they cannot be interpreted directly as difference from a population mean. However, mean WOMAC scores from a large population-based sample of healthy adults have been published (Bellamy et al. 2011), giving benchmark values for comparison (Table 1).

[Appendix 3](#) includes the complete text of the WOMAC as it appears to subjects in the study.

#### 5.4.1. MPCl for WOMAC Scales and Responder definition

The minimum perceptible clinical improvement (MPCl) for WOMAC scales are defined according to the WOMAC User Guide (Bellamy 2012) as follows:

- WOMAC Pain: 9.7 nu (normalized units)
- WOMAC Stiffness: 10.0 nu
- WOMAC Physical Functioning: 9.3 nu

For each of the three WOMAC scales the responders are the subjects with the decrease from baseline greater than or equal to the corresponding MPCl.

## 5.5 SF-36 Health Survey version 2

The SF-36v2 is a self-reported survey of general HRQL with a 4-week recall period. Its 36 questions measure eight underlying health domains, and responses to sets of questions are combined and scored to yield scale scores for each domain, as shown in Table 2.

**Table 2: SF-36v2 Scales and Number of Questions in Each Scale**

Scale Name	Acronym	Number of SF-36v2 questions combined into scale score
Physical Functioning	PF	10
Role Limitations due to Physical Health	RP	4
Bodily Pain	BP	2
General Health Perceptions	GH	5
Vitality	VT	4
Social Functioning	SF	2
Role Limitations due to Emotional Problems	RE	3
Mental Health	MH	5

Note: The health transition question (item 2 on the SF-36v2, as shown in [Appendix 4](#)) is not used in the calculation of SF-36v2 scales.

Additionally two summary component scores are calculated from domain scores (Physical Component Summary Scale [PCS] and the Mental Component Summary Scale [MCS]). They each draw information from all eight scales, with weights derived from the population-based sample. The PCS depends most heavily on the PF, RP, BP and GH scales, while the MCS mainly reflects the MH, RE, SF, and VT scales.

Raw scores range from 0 to 100 with higher scores indicating better health. Domain scores are calculated from raw scores such that domain scores have a mean of 50 and SD of 10. The PCS and MCS summary component scores also have mean of 50 and SD of 10 to allow comparisons with domain scores.

[figure not shown]
Scoring the SF-36 version 2 is accomplished using T-score Based scoring software from QualityMetric Inc ([Maruish 2011](#)). T-score Based scoring is standardized across the SF family of adult tools using the means and standard deviations from the 2009 U.S. general population. The T-score Based scores in the U.S. general population have a mean of 50 and a standard deviation of 10. The PCS and MCS are both expressed as norm-based scores on the

same metric as the scales, and can be interpreted in the same manner. The scoring process is summarized in Figure 1.

The main advantage of T-score Based scoring of the adult SF tools is easier interpretation. By using the T-score Based scoring method, the data are scored in relation to U.S. general population t-scores. Therefore, all scores obtained that are below 40 can be interpreted as 1 standard deviation below the U.S. general population t-score and scores above 60 can be interpreted as 1 standard deviation above the U.S. general population t-score. Because the standard deviation for each scale is 10, it is easier to see exactly how far above or below the mean a score is in standard deviation units (10 points = 1 standard deviation unit).

[Appendix 4](#) includes the complete text of the SF-36 as it appears to subjects in the study.

**Figure 1: Process for scoring SF-36v2 Health Domain Scales and Component Summary Measures**

### 5.5.1 MIC for SF-36v2 Scales and Responder definition

The Minimally Important Change (MIC) is the smallest change over time in an individual patient's score that represents a clinically significant change in their health status. Using a distributional approach with a US general population sample, MICs have been established for the SF-36v2 as: PF, 3.5 points; Role-Physical, 3.2; Bodily Pain, 4.5; General Health, 5.7; Vitality, 5.5; Social Functioning, 5.0; Role-Emotional, 3.8; Mental Health, 5.5; PCS, 3.1; and MCS, 3.8.

## 5.6 Percent of Predicted 6-Minute Walk Test Distance

To calculate the percent predicted 6MWT value, the following formula will be applied ([Gibbons et al. 2001](#)).

$$X_i = \frac{X_{0i}}{868.8 - (2.99 \times \text{Age}) - (74.7 \times \text{Gender})} * 100$$

where  $X_i$  is the percent predicted 6MWT result at time  $i$  for subject  $X$ ,  $X_{0i}$  is the 6MWT result (in meters) at time  $i$  for subject  $X$ , and Gender is equal to 0 if the subject is male or 1 if the subject is female. Age at the study visit will be used for the calculation for the duration of the study.

## 5.7 Events To Monitor

**Injection Site Reaction (ISR):** Defined by preferred terms under the Medical Dictionary for Regulatory Activities (MedDRA) high-level term (HLT) “Injection site reaction”.

**Immunogenicity AE:** Defined using relevant PTs in the narrow SMQs for “Hypersensitivity”.

**Hyperphosphataemia AE:** Defined by using PTs: “Hyperphosphataemia”, “Blood phosphorus increased”.

**Ectopic calcification related AE:** There is no available SMQ. Ectopic calcification related AE is defined using a MedDRA search of ‘calcification’.

**Gastrointestinal AEs:** i.e. nausea, vomiting, abdominal pain, diarrhea. Defined using PTs in the narrow SMQ “Gastrointestinal nonspecific inflammation and dysfunctional conditions”.

**Restless leg syndrome AE:** Defined by PTs “Restless legs syndrome”, “Restlessness”, “Akathisia”, “Sensory disturbance”, “Psychomotor hyperactivity”, “Limb discomfort”, “Neuromuscular pain”, “Formication”.

See search criteria in [Appendix 5](#).

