7.5.3 Safety Measurements

7.5.3.1 Adverse Events

The investigator will inquire about AEs at all subject visits by asking the subject a question such as: "How have you been feeling since your last visit?" All AEs, whether observed by the investigator or reported by the subject, will be recorded on the appropriate AE page of the eCRF and as appropriate on the SAE form, from the time the subject signs the informed consent through their EoT Visit or final Safety Follow-up TC as outlined in Section 7.1. The Safety Follow-up telephone call (TC) that occurs 4 weeks (+5 days) after a subject's EoT Visit, will collect information on whether KRN23 treatment has been started through another mechanism and, if not, any ongoing or new AEs, SAEs, or concomitant medications. If the subject is not continuing KRN23 therapy under commercial use or another mechanism at that time, then site personnel will initiate a subsequent Safety Follow-up TC 8 weeks (+ 5 days) after the ET Visit to collect information on whether KRN23 treatment has been started through another mechanism and, if not, any ongoing or new AEs, SAEs, or concomitant medications. The determination, evaluation, reporting, and follow-up of AEs will be performed as outlined in Section 8.5. At each visit and the follow-up telephone call, subjects will be asked about any new or ongoing AEs since the previous visit. Assessments of AEs will occur at each visit to the investigational site, all HH visits, and the follow-up telephone call as outlined in Section 7.1. All AEs will be evaluated to determine whether they meet the criteria of being a DLT (Section 7.5.3.13).

Clinically significant changes from baseline in physical examination findings, vital signs, clinical laboratory parameters, renal ultrasounds, eGFR, ECHO, and ECGs will be recorded as AEs or SAEs, if appropriate.

Any laboratory test results that fall outside the laboratory normal range will be considered abnormal. The investigator will indicate if such values are clinically significant (CS) or not (NCS). All laboratory tests with clinically abnormal values (i.e., beyond those expected for subjects with XLH of this age group) should only be recorded as an AE if symptomatic, if potentially life-threatening without symptoms, or if deemed appropriate by the investigator.

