7.5.3.13 Dose-limiting Toxicity

A DLT is defined as the occurrence of any of the following:

- A Grade 3 or higher toxicity (based on the National Cancer Institute's (NCI) Common Terminology Criteria for Adverse Events [CTCAE] Version 4 ([NCI 2010](#)) that occurs during treatment and is considered to be either possibly, probably, or definitely related to study drug
- A confirmed serum phosphorus level of ≥ 6.5 mg/dL (defined as hyperphosphatemia) at any time after dosing

If a subject experiences a DLT, the planned dosing for that subject will be evaluated by the investigator and medical monitor. The outcome of this investigation will determine the subjects' continuation or withdrawal from the study.

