7.6.2.8.2 Clinical Laboratory Evaluations

Clinical laboratory data will be summarized by the type of laboratory test. Reference ranges and markedly abnormal results (specified in the SAP) will be used in the summary of laboratory data. Descriptive statistics will be calculated for each laboratory analyte at Baseline and at each scheduled time point. Changes from baseline results will be presented in pre- versus post-treatment cross tabulations (with classes for below, within, and above normal ranges). A listing of subjects with any markedly abnormal laboratory results will be provided. The frequency and percentage of subjects who experience abnormal clinical laboratory results (i.e., outside of reference ranges) and/or clinically significant abnormalities will be presented for each clinical laboratory measurement. A list of reference ranges standardized across clinical laboratories will be provided.

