## 8 STATISTICAL METHODS OF ANALYSIS

### 8.1 General Principles

The statistical analyses will be reported using summary tables, figures, and data listings. Statistical tests will be 2-sided at the alpha=0.05 significance level and 2-sided 95% confidence interval will be used. All p-values will be presented as nominal p-values. No adjustment on multiplicity will be made. Continuous variables will be summarized with means, standard deviations, standard errors, medians, Q1, Q3, minimums, and maximums. Categorical variables will be summarized by counts and by percentages of subjects in corresponding categories. No imputation on missing data will be made, unless stated otherwise. All data obtained from the CRFs as well as any derived data will be included in data listings.

The Week 24 analysis will be performed when all patients enrolled in the study have completed the Week 24 visit or have discontinued the study. The final analysis will be conducted when all patients enrolled in the study have completed the Week 72 visit or have discontinued the study.

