### **8.6.2 Safety Lab Parameters**

The descriptive statistics will be provided for lab safety parameters (chemistry, hematology, and urinalysis parameters, GFR, HAHA). In addition, shift tables will be provided for HAHA (with categories Yes/No) and for amylase. For amylase, the following categories will be used:

- Normal
- Grade 1: 1 - 1.5 x ULR
- Grade 2: 1.5 – 2 x ULR
- Grade 3: 2 – 5 x ULR
- Grade 4: > 5 x ULR.

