## 8.8 Endpoints

### 8.8.1 Pharmacodynamic Endpoints

The number and proportion of subjects with serum phosphorus level in the normal range ( $\geq 2.5$  and  $< 4.5$ ) at each time point will be provided, along with the two-sided 95% confidence intervals, obtained using the GEE model described in Section 8.1.1. An overall summary of the number and proportion of patients who ever reached the normal range over the duration of the study will also be provided. Additional analyses of serum phosphorus including observed values, change from baseline, percent change from baseline over time will be summarized.

For the final analysis, the primary PD endpoints at all post-baseline visits will be compared to baseline using the GEE model described in Section 8.1.1, and the primary statistical comparison will be between the levels at baseline and week 72.

For the interim analysis, the primary PD endpoints at all post-baseline visits prior or at week 24 for all patients will be compared to baseline using the GEE model, and the primary statistical comparison will be between the levels at baseline and week 24.

For all primary PD endpoints descriptive statistics of observed values and of changes from baseline at each visit will be provided.

Graphs showing the change over time in key PD parameter for both observed measure and the change from baseline will be provided. The relationship between various PD parameters as well as KRN23 concentrations may be examined.

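### The SAP does not carry over the protocol's below/within/above table or DLT count for serum phosphorus, and its only named hyperphosphataemia count depends on AE reporting

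*SAP*

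**What the plan says.** **SAP.**
- Section 5.7 lists a hyperphosphataemia AE, "Defined by using PTs": Hyperphosphataemia and Blood phosphorus increased. Appendix 5 repeats the two terms without a laboratory limit, and 8.6.1 carries the category into the AE summaries. DLTs are not among those summaries.
- Section 4.2 classifies subjects by whether serum phosphorus at any time after dosing is in the normal range "or outside the normal range". Section 8.8.1 then reports "The number and proportion of subjects with serum phosphorus level in the normal range" at each time point, plus the number who ever reached it.
- Section 8.6.2, on laboratory safety, states: "In addition, shift tables will be provided for HAHA (with categories Yes/No) and for amylase". Amylase gets five categories; phosphorus gets none. In Appendix 1 phosphorus appears only as a pharmacodynamic (PD) endpoint, not in the safety chemistry row.

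**Protocol.**
- Section 7.6.2.8.2 plans pre- versus post-treatment laboratory cross-tabulations "with classes for below, within, and above normal ranges", and the frequency and percentage of subjects with abnormal results for each laboratory measurement. Phosphorus is in the safety chemistry panel (Table 7.5.3.6.1).
- Section 7.6.2.8 plans the incidence and frequency of DLTs. One DLT criterion (7.5.3.13) is "A confirmed serum phosphorus level of ≥ 6.5 mg/dL (defined as hyperphosphatemia) at any time after dosing".
- Section 7.5.3.1 says that clinically abnormal laboratory values "should only be recorded as an AE if symptomatic, if potentially life-threatening without symptoms, or if deemed appropriate by the investigator".

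**The concern.** High phosphorus is the on-target risk that the protocol itself identifies. Section 5.2.3 attributes the major toxicological findings, such as mineralization, to phosphorus raised above normal. Section 7.4.5 expects the safety profile to follow from the PD effect alone. A value above 4.5 mg/dL is also the protocol's own condition for possible downward titration (7.1), and long-term safety is the first primary objective.

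For that risk, the one count the SAP names passes through a reporting filter. An asymptomatic value above 4.5 mg/dL gets a preferred term only if it is potentially life-threatening or the investigator thinks it appropriate to record. The phosphorus endpoint cannot make up the difference, because its second class joins subjects who stayed too low with subjects who went too high. These are opposite findings, one a lack of effect and the other an excess of it. A report built from the SAP's category tables could show few or no hyperphosphataemia AEs and still leave unanswered how many subjects exceeded the upper limit.

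**Working it through.** The plan states no figure on this point, so there is none to reproduce. The check traces where a high phosphorus value could be counted, then asks what the two-class rule can reveal.

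**1. Routes by which an asymptomatic value above 4.5 mg/dL could be reported**

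| Route | Source | Directional laboratory count? |
|---|---|---|
| Hyperphosphataemia event to monitor | SAP 5.7, 8.6.1 | No; AE terms only |
| In range or outside | SAP 4.2 | No; low and high merged |
| In range per visit, and ever in range | SAP 8.8.1 | No; a subject once in range who later overshoots still counts as ever in range |
| Named laboratory shift tables | SAP 8.6.2 | No; anti-KRN23 antibody (HAHA) and amylase |
| Clinically significant laboratory changes | SAP 4.1 | Rests on judgement; 8.6.2 gives no method |
| By-visit maximum and listings | SAP 8.1 | Value visible, not counted |
| Three-class table and per-analyte abnormality counts | Protocol 7.6.2.8.2 | Three-class table yes; not specified for phosphorus in the SAP |
| DLT incidence | Protocol 7.6.2.8, 7.5.3.13 | Yes, at confirmed 6.5 mg/dL or more; not in the SAP |

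**2. What the merged class can say**

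If k of n subjects are outside, the number above range can be any integer from 0 to k. With n = 20 (protocol 7.6.4) and, for illustration, k = 5, that is 0/20 = 0% to 5/20 = 25%. Suppose these are the subjects outside at one visit, where the minimum is below 2.5 and the maximum above 4.5 mg/dL. The range then narrows only to 1 to 4 subjects (5% to 20%). Maxima from different visits cannot be added up, because the same subject may supply several of them.

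**3. Whether the data exist**

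SAP Appendix 1 schedules phosphorus at Weeks 2, 4, 6, 8, 10, 12, 24, 26, 28, 36, 38, 40, 48, 50, 52, 60 and 72. That is 17 post-baseline time points, 7 of them by Week 24. Six (Weeks 2, 6, 10, 26, 38, 50) fall two weeks after a scheduled dose. The count needs no new data.

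**4. Precision of the added count**

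Exact (Clopper-Pearson) two-sided 95% limits:
- 0/20: upper limit 1 − 0.025^(1/20) = 16.8%
- 1/20: 0.1% to 24.9%
- 2/20: 1.2% to 31.7%
- 0/25 (the SAP's approximate sample size): upper limit 1 − 0.025^(1/25) = 13.7%

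The chance of seeing at least one such subject among 20 is 1 − (1 − p)^20, which is 64%, 88% and 96% for true rates p of 5%, 10% and 15%. These rates are assumptions; the documents give none.

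**5. The upper bound**

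SAP 4.2 and protocol 7.6.1.2 include 4.5 mg/dL in the normal range. SAP 8.8.1 requires less than 4.5. A value of exactly 4.5 is in range under one and not under the other. If above is defined as greater than 4.5, that value fits neither class under 8.8.1.

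**The case against.** The strongest reply is that the SAP's silence does not cancel a protocol analysis. Protocol 7.6.2.1 says the SAP expands the protocol's analyses and that deviations will be noted in the study report. On that view the three-class table, the abnormality counts and DLT incidence are still planned. A reader might infer from the SAP that asymptomatic over-correction is counted nowhere, and the documents do not support that. Besides the protocol analyses, SAP 4.1 lists clinically significant laboratory changes separately from AEs. SAP 8.1 says "Continuous variables will be summarized with means, standard deviations, standard errors, medians, Q1, Q3, minimums, and maximums", so a high value would show as a by-visit maximum, and all data are listed.

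Three further points have force.
- The AE rule has other routes. Protocol 7.5.3.14 sends clinically significant changes to the AE page, and 7.5.3.6 requires capture of abnormalities that lead to interruption, discontinuation or corrective therapy.
- SAP 8.6.2 names two laboratory shift tables without saying that there will be no others, and defining an AE category by preferred terms is ordinary practice.
- The SAP details the protocol dated 05 September 2014, while the protocol in hand is Amendment 2. One cannot say that the analyses were deliberately dropped. The amendment summaries, however, do not list the cross-tabulations or DLT incidence as new.

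What remains is this. Protocol 7.6 calls its statistical text a guide and leaves detailed methods to the SAP. Section 7.6.2.8.2 leaves the markedly abnormal limits to the SAP, which sets none for phosphorus. The other AE routes depend on investigator judgement or on action taken. Maxima and listings show values without counting subjects.

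**Conclusion.** The point holds as a gap between the two documents and a weak classification rule within the SAP. It does not show that high phosphorus would go unseen. The SAP's only named hyperphosphataemia count depends on AE reporting. Its two-class rule cannot separate over-correction from under-correction, and the protocol's directional table and DLT incidence are not carried over for phosphorus. With 5 of 20 subjects outside, the number above range is undetermined between 0 and 5.

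How many subjects will exceed 4.5 mg/dL cannot be predicted from the documents. Protocol 7.4.5 reports that none did in KRN23-INT-001, at doses up to 0.6 mg/kg, so the count here may be zero. A zero from laboratory values in 20 subjects, with its 16.8% upper limit, would still say more than a zero from AE terms. The conclusion assumes that the reported tables follow the SAP as written; if the protocol's tables are produced as well, most of the gap closes. The change is a worthwhile, cheap improvement.

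**What to change.** - **SAP 4.2 and 8.8.1:** first reconcile the upper bound so that exactly 4.5 mg/dL is classed the same way in both sections. Then divide the out-of-range class in 4.2 into below and above, and report below, within and above at each time point in 8.8.1.
- **SAP 8.6.2:** add a low/normal/high shift table for serum phosphorus. Add counts of subjects ever above 4.5 mg/dL and of subjects with a confirmed value of 6.5 mg/dL or more (the protocol's DLT criterion), each with an exact 95% interval. Include unscheduled samples, which SAP 7.5 already admits to shift tables.
- **SAP 8.6.1:** add DLT incidence.
- **SAP 5.7:** keep the preferred-term category as a separate AE summary.

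The cost is two or three extra tables from data already collected, with no change to study conduct or dosing. The downside is that the hyperphosphataemia count may look less favourable than the AE-based one.
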